LD	Linkage Disequilibrium (LD) is a measure of association between alleles at different loci.				
OR	Odds ratio, the ratio of the odds of cases having the suspect genotype to the odds of controls having the suspect genotype (or: the odds of being a case given carriage of the suspect genotype divided by the odds of being a case given the absence of the suspect genotype).				
PGx population	Consists of subjects in the clinical intent to treat (ITT) population who consent to a genetic study and provide an adequate DNA sample for genotyping.				

PGx analysis population	The collection of subjects from the clinical studies under investigation who provided written informed consent for genetic research, provided a blood sample for genotyping that was successfully genotyped for at least one of the genetic markers under study, and passed a subject data quality control check.
Polymorphism	A genetic locus at which there is a difference in DNA sequence among individuals (i.e. which has 2 or more alleles in the population)
QC	Quality Control
RAP	Reporting and analysis plan
Risk Genotype	The genotype of an genetic marker that is associated with diarrhea case status
SNP	Single nucleotide polymorphism

Trademark Information

Trademarks of the GlaxoSmithKline group of companies

VOTRIENTTM

Trademarks not owned by the GlaxoSmithKline group of companies

None

1. INTRODUCTION

Pazopanib (VOTRIENT[™], GlaxoSmithKline) is an oral angiogenesis inhibitor targeting vascular endothelial growth factor receptors (VEGFR) -1, -2, and -3, platelet-derived growth factor receptors, and the stem cell factor receptor, c-Kit. Pazopanib is approved in multiple countries for the treatment of advanced renal cell carcinoma (RCC). Pazopanib has demonstrated clinical activity against multiple tumour types, and its safety profile is generally acceptable and tolerable. The most commonly observed adverse reactions (≥20%) in the 586 patients with RCC were diarrhoea, hypertension, hair color change, nausea, fatigue, anorexia, and vomiting. The prevalence of diarrhoea in the phase III RCC trial (N=290) was 52% for all grades and ~4% for grade 3 and above in pazopanib treated subjects, compared to 9% for all grades and <1% for grade 3 and above in placebo treated subjects (N=145), respectively [Sternberg, 2010] .Up to date, the mechanism of pazopanib related diarrhoea.

Diarrhoea is one of the most common side effects of cancer treatment and can be a serious and debilitating complication. Careful analysis and understand of the causative factors can help on a more accurate management and early intervention, and possibly prevent severe complications for patients.

Several pathophysiological mechanisms for potential drug-induced diarrhoea have been hypothesized. Evidence suggests that drug induced diarrhoea is probably a multifactorial process that results in absorptive and secretory imbalances in the bowel [Abraham, 2007]. Cancer treatment (ie. chemotherapy drugs) can cause diarrhoea by damaging immature epithelial cells in the crypt which results in subsequent mature enterocytes being functionally impaired, decreasing their absorptive capacity or by disrupting the integrity of the intestinal mucosa through inflammatory and ulcerated lesions. Additionally, a disruption to normal active ion absorption in the small intestine can lead to an excess of water and electrolytes [Stein, 2010]. Identification of genes that act on these pathophysiological pathways may help our understanding of the pazopanib-related diarrhoea mechanism and, thus, patient susceptibility to it.

The purpose of this investigation is to determine if observed diarrhoea events seen in pazopanib treated RCC patients may be associated with genetic risk factors. Genetic markers in 38 candidate genes and markers from Illumina Human1M DNA Analysis BeadChip will be evaluated. See Section 13.1 for specific information on the candidate genes investigated.

Patients who consented and provided a DNA sample from the following clinical trials are included in this genetic investigation: VEG102616, VEG105192, and VEG107769.

This document describes the analyses planned to explore the impact of genetic variation on diarrhoea in pazopanib treated subjects through a primary analysis on defined diarrhoea case-control (CC) endpoint, and a secondary analysis on ordinal endpoint by using diarrhoea toxicity grade levels. As these data are pooled from three clinical trials, special consideration will be taken with respect to relevant clinical factors. All analyses are exploratory with respect to the genetic markers being evaluated.

This document contains a brief summary of the study design followed by descriptions of the analysis populations, analysis variables, statistical methods and possible ways to summarise the data that will comprise the analysis.

2. STUDY OBJECTIVES AND ENDPOINT

2.1. Study Objective

The objective of this analysis is to investigate if genetic markers from 38 candidate genes or other markers from across the genome are associated with incidence of diarrhoea in RCC patients treated with pazopanib in studies VEG102616, VEG105192 and VEG107769.

2.2. Study Endpoints

The primary endpoint is the diarrhoea outcome status defined as:

- Case a patient who experienced a minimum of Grade 2 diarrhoea based on the National Cancer Institute Common Toxicity Criteria v3.0 (Table 2-1) during pazopanib treatment.
- **Control** a patient who received pazopanib for a minimum of 42 days, but never developed diarrhea. Forty-two days was the median time to first diarrhea event in patients treated with pazopanib in the studies.

Note that patients who experienced diarrhoea episodes at grade 1 are not included in the case-control analysis.

The secondary endpoint is diarrhoea toxicity grade levels from 1 to 5 (Table 2-1) and grade 0 for the control described above, defined as an ordinal categorical variable. As the number of subjects who experienced high diarrhoea toxicity grade (Grade 3+) is small, it may be possible to pool subjects with Grade 2-5 into a single category for the purposes of this analysis.

Grade	Description
1	Increase of <4 stools per day over baseline; mild increase in ostomy output compared
	to baseline
2	Increase of 4 – 6 stools per day over baseline; IV fluids indicated <24hrs; moderate
	increase in ostomy output compared to baseline; not interfering with activities of daily
	living
3	Increase of ≥7 stools per day over baseline; incontinence; IV fluids ≥24 hrs;
	hospitalization; severe increase in ostomy output compared to baseline; interfering
	with activities of daily living
4	Life-threatening consequences (e.g., hemodynamic collapse)
5	Death

Table 2-1 NCI's Common Toxicity Criteria v3.0 for Diarrhoea*

1. *Diarrhoea includes diarrhoea of small bowel or colonic origin, and/or ostomy diarrhoea.

3. STUDY DESIGN

Data included in this analysis were derived from clinical studies VEG102616, VEG105192, and VEG107769, all pazopanib monotherapy studies in subjects with RCC.

The clinical data used will be from the Integrated Safety Summary (ISS) for these three studies. The ISS data came from the SAC analyses for VEG102616 and VEG105192, with data cutoffs of April 2008 and May 2008 respectively. Interim data for VEG107769 was included in ISS with a date cutoff of May 2008.

A brief description of the studies, with the number of subjects available for genotyping is provided in Table 3-1.

	ITT	Pazopanib treated ITT	PGx		
Study	Population1	Population1	Population2	Study Design	Description
VEG102616	225	225	164	A phase II, pazopanib monotherapy, randomized discontinuation design study	To determine the efficacy and safety of pazopanib in subjects with locally recurrent or metastatic clear-cell renal cell carcinoma. Subjects received pazopanib administered orally at a daily dose of 800 mg.
VEG105192	435	290	182	A phase III, randomized, double blind, placebo- controlled, multi- center study	Eligible patients were stratified and randomized in a 2:1 ratio to receive either 800 mg of pazopanib once daily or matching placebo.
VEG107769	71	70	51	A phase III, open-label, pazopanib monotherapy, multi-center study	An open-label, extension study, to evaluate safety and efficacy of pazopanib in patients who randomized into study VEG105192 and experienced progressive disease after receiving placebo as the study treatment. Subjects receive 800 mg pazopanib once daily.
Total	731	585	397		

Table 3-1Description of the Clinical Studies

1. The ITT Population consists of subjects who were enrolled in studies with intent to treat.

2. The PGx Population is comprised of subjects from the ITT population who provided written informed consent for PGx research and an adequate DNA sample for genotyping.

4. PLANNED ANALYSES

Primary analysis is to test association of case-control endpoint with each genetic marker. Secondary analysis is to test association of ordinal endpoint with each genetic marker. The analysis will be conducted using pazopanib treated patients of all racial groups pooled, and will use genetic ancestry information (derived from Principal Component analysis of the genotype data) to control for potential population stratification.

5. SAMPLE SIZE CONSIDERATIONS

The clinical studies being used in this analysis were not prospectively designed to address genetic research hypotheses and, thus, did not benefit from prospective sample size calculations. Instead of calculating the sample size necessary to attain a certain statistical power, the anticipated sample size will be used to estimate power under a variety of potential experimental scenarios and genetic models.

5.1. Retrospective Power Calculations

The power to detect a significant statistical genetic association is dependent upon several factors, such as the population prevalence of the event, the frequency of the risk genotype in cases, the size of the genetic effect, and the number of subjects analyzed. Basic retrospective power calculations were conducted to inform what kinds of genetic effects could be found given the observed numbers of diarrhoea cases in the clinical studies. These power calculations might be over-estimated given the assumption that no covariates are included in the model and that the causal variant itself will be assessed (as opposed to a variant in partial linkage disequilibrium with the causal variant).

Table 5-1 presents the subject count at each toxicity grade of diarrhoea in pazopanib treated ITT and PGx population. Power was calculated for diarrhoea case-control status, based on the expected number of RCC patients in pazopanib treated PGx population. The power was estimated assuming a 2 degree of freedom genotypic test conditional on the underlying genetic model being additive, dominant or recessive, respectively. These calculations assumed a type I error rate of 3.1×10^{-4} , the significance threshold with Bonferroni correction for Tier 1 markers (see Section 7.6 for the definition of Tier 1 markers). The plots show the relationship between statistical power and the odds ratio (OR) of the two homozygotes (Figure 5-1). The different curves correspond to power estimates assuming six different risk allele frequencies (RAFs).

Table 5-1	Summary of diarrhoea for pazopanib treated subjects in VEG102616,
	VEG105192 and VEG107769

Diarrhoea AE grade	ITT (%)	PGx population (%)			
0*	266 (45%)	156 (39%)			
1	202 (34%)	151 (38%)			
2	95 (16%)	78 (20%)			
≥3	21 (3.6%)	12 (3%)			
Missing data	2 (0.3%)	0			
Total	586	397			
1. * Without consideration of treatment time for pazopanib					

With 90 diarrhoea cases and 132 controls as defined in Section 2.2, there are many combinations of genotypic models, risk allele frequencies and odds ratios, that may lead to good statistical power (>80%) to detect an effect, especially if the dominant or additive models are true and if the risk allele is relatively common in the study population (i.e., MAF \geq 20% with a genetic effect OR \geq 4). The power to detect significant associations with SNPs from GWAS will be considerably reduced in comparison given approximately 1 million markers tests.

Figure 5-1 Power Estimation

Power @ alpha=0.00031 & nca=90, nco=132, npc=0

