7.6. Multiple Comparisons and Multiplicity

A set of p-value thresholds will be used to claim significant association. To establish these thresholds, control of the family-wise type I error for multiple tests will be calculated as described below. All genetic markers are categorized into three tiers based on the prior biological information. The first tier includes 53 functional markers from the candidate genes. The second tier consists of the rest of the markers (~1300 SNPs) in the candidate genes. The third tier will comprise all other Illumina 1M markers that do not map to the 38 candidate genes (~1M markers). A family-wise error rate of 0.05 is allocated evenly to the three tiers, that is, 0.0167 (determined from 0.05/3). The

significant p-value thresholds for the first, the second and third tiers are calculated using the Bonferroni correction, which is 0.0167 / (number of markers), for each analysis at each tier. Linkage disequilibrium among markers within each category will be taken into account and an effective number of tests in Tier 1 & 2 can be estimated for the purpose of the multiple test adjustment [Moskvina, 2008]. Once the actual number of markers to be analyzed within each category has been determined, a per-marker significance level will be calculated and applied to the statistical test results.

Genetic markers that satisfy nominal p-value thresholds of ≤ 0.05 , ≤ 0.01 , and $\leq 10^{-4}$ in the first, second and third tiers, respectively, will also be summarized as suggestive evidence for association; which will be further evaluated in future studies.

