10.5. Evaluation of Genotypic Association

Logistic regression will be used to examine the effect of marker genotypes on the casecontrol status for diarrhoea (See Section 2.2 for diarrhoea case-control status definition). Prior to the PGx analysis, a model which includes necessary non-genetic independent variables that may influence the endpoints will be identified using the PGx Analysis Population (see Section 7.2 for the covariates that will be evaluated). The model may be reduced, if needed, to include only significantly predictive non-genetic terms (p<0.05) prior to beginning the genetic analyses. Multiple analyses will be run, evaluating each genetic marker, one at a time, while keeping covariates used constant throughout all analyses.

Proportional odds model, adjusting for some of the covariates, will be used to explore the effect of selected or all markers' genotypes on the ordinal diarrhoea toxicity grade levels if it is necessary. One hundred fifty one subjects classified as grade G1 diarrhoea toxicity level that are excluded in case-control analysis will be included in this analysis. The expected number of subjects in this analysis, by grade, is: 132 G0, 151 G1, and 90 G2-G4 (combined) subjects. The proportional odds assumption will be evaluated for the resulting three levels of diarrhoea toxicity. The analyses will be performed using ordinal logistic regression.

The following model will be fitted to identify the genetic effect.

Endpoint = PC1 + PC2 + ... PCn + Covariates + Genotype -- model (1)

The endpoint variables are those listed in Section 7.1. Covariates are those listed in Section 7.2. PC1 represents the first principal component based on the analysis of genome-wide markers, PC2 represents the second principal component and so on. The number of principal components necessary to characterize subject ancestry, n, will be analytically determined; for many datasets an n of 2 or 3 is adequate. An additive genetic model is used here. *Genotype* codes for the number of copies (0, 1, or 2) of the minor (less frequent) allele and will be evaluated as a numeric variable.

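### Section 5.1 states power for a 2-df genotypic test, but the planned test in Section 10.5 is a 1-df additive test, so the stated power belongs to a test that will not be run

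*SAP*

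**What the plan says.** Section 5.1 gives retrospective power for the case-control endpoint: "The power was estimated assuming a 2 degree of freedom genotypic test conditional on the underlying genetic model being additive, dominant or recessive". The group sizes are given there ("With 90 diarrhoea cases and 132 controls as defined in Section 2.2"), and the label of Figure 5-1 repeats them with the significance level: "Power @ alpha=0.00031 & nca=90, nco=132, npc=0". The effect axis is the OR between the two homozygotes. The closing paragraph says that many scenarios may exceed 80% power, especially for dominant or additive effects with MAF of at least 20% and OR of at least 4. Two reasons for over-estimation are listed: no covariates, and the causal variant being typed directly.

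Section 10.5 sets out the test that will be run. The method is logistic regression ("Logistic regression will be used to examine the effect of marker genotypes on the casecontrol status for diarrhoea"). On the genetic term it says "An additive genetic model is used here", and the genotype variable "codes for the number of copies (0, 1, or 2) of the minor (less frequent) allele and will be evaluated as a numeric variable".

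**The concern.** One numeric genotype term is a 1-df test. A 2-df test leaves the three genotype risks free. It pays for the extra degree of freedom when the truth is additive, and gains when the truth departs from additivity. Power for one test is therefore not power for the other, and the difference changes sign with the true genetic model.

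Section 5.1 exists to tell the reader which genetic effects this sample could detect, and its curves are what a reader would use to interpret a null result. Read as they stand, they show the planned test as better than it is for recessive effects and for dominant effects of common alleles, and worse than it is for additive effects. The over-estimation caveat in Section 5.1 does not mention this, and it points the wrong way for additive effects.

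**Working it through.** **Inputs.** From the SAP: 90 cases and 132 controls, alpha 3.1×10⁻⁴, homozygote OR scale, three true models (Section 5.1 and Figure 5-1); one numeric 0/1/2 term (Section 10.5). Assumed: RAF from 0.1 to 0.5, because the six values are not in the readable text; and the population in which Hardy-Weinberg proportions hold, which the SAP does not state. Three baselines were used: HWE in controls, and HWE in the source population at a prevalence of 23% (90/397 = 22.7%, Table 5-1) or 40.5% (90/222).

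**The plan's own figures first.** On alpha, Section 7.6 says "A family-wise error rate of 0.05 is allocated evenly to the three tiers, that is, 0.0167". With 53 Tier 1 markers, (0.05/3)/53 = 3.14×10⁻⁴, which agrees with the stated 3.1×10⁻⁴. On the >80% statement, the 2-df test at dominant OR 4, RAF 0.2 gives 83–86%, which agrees. Additive with homozygote OR 4 does not reach 80% with either test (table below). If OR 4 is per allele (homozygote OR 16), additive power is about 99%. That is a question of OR scale, separate from the degrees of freedom. The curves themselves cannot be reproduced, because the figure is not shown.

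**Formulas.** Genotype ORs for 0, 1, 2 risk alleles: additive (1, √OR, OR), dominant (1, OR, OR), recessive (1, 1, OR). With case and control genotype frequencies p_i and q_i, n₁ = 90, n₂ = 132, N = 222:

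- 2 df: λ₂ = n₁n₂ Σ (p_i − q_i)² / (n₁p_i + n₂q_i); critical value 16.16.
- 1 df: λ₁ = (n₁n₂/N) d²/V, where d is the case-control difference in mean allele count and V its pooled variance; critical value 13.01.
- Power is the noncentral chi-square tail beyond the critical value.

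**Worked case: dominant, OR 4, RAF 0.4, HWE in controls.**

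- Controls: 0.36, 0.48, 0.16. Cases: (0.36, 1.92, 0.64)/2.92 = 0.123, 0.658, 0.219.
- Pooled expected counts: 58.6, 122.5, 40.8.
- λ₂ = 11,880 × (0.0560/58.6 + 0.0315/122.5 + 0.0035/40.8) = 15.4, so power is 51%.
- d = 1.096 − 0.800 = 0.296 and V = 0.442, so λ₁ = 53.5 × 0.0876/0.442 = 10.6 and power is 36%.

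The additive term loses about a third of the noncentrality. Under additive truth (OR 4, RAF 0.2) both noncentralities are 9.8, so only the degrees of freedom differ: 23% for 2 df and 32% for 1 df.

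**Results over the three baselines.** These are by simulation, with the likelihood-ratio or Pearson statistic for 2 df. All are for homozygote OR 4.

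| True model | RAF | 2-df power | Planned 1-df power |
|---|---|---|---|
| Additive | 0.2 | 15–23% | 23–32% |
| Recessive | 0.3 | 15–47% | 5–26% |
| Recessive | 0.5 | 68–84% | 49–74% |
| Dominant | 0.1 | 53–79% | 61–83% |
| Dominant | 0.2 | 83–86% | 83–85% |
| Dominant | 0.4 | 53–76% | 36–61% |
| Dominant | 0.5 | 25–55% | 12–31% |

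Within each baseline the direction is the same, except at dominant RAF 0.2, where the two tests are about equal. Some scenarios cross the SAP's 80% line: with HWE in controls, recessive OR 4 at RAF 0.5 goes from 83–84% to about 74%, and dominant OR 6 at RAF 0.4 from 82–87% to about 60%.

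**The case against.** **The consequence is small.** The calculation is retrospective and sets no sample size (Section 5), all analyses are exploratory (Section 1), and the wording in Section 5.1 is hedged. This stands. It limits the point to a correction of the stated power.

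**The main prose claim survives at its boundary.** At dominant OR 4, MAF 20%, the planned test still gives 83–85%. The closing paragraph makes no specific claim for recessive effects. Where it is hard to support (additive homozygote OR 4, dominant at RAF 0.4–0.5), it is already hard to support with the 2-df test. This stands too. A reader might infer that every statement in Section 5.1 about detectable effects is wrong because of the degrees of freedom; the documents do not support that.

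**The size depends on the baseline.** Dominant OR 6 at RAF 0.4 has 1-df power of about 60% with HWE in controls but 90% with HWE in the source population at 40.5% prevalence. This stands, and is why the results are ranges.

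**A 2-df test might be intended after all.** The heading of Section 10.5 refers to genotypic association, the abbreviation list includes Fisher's exact test, and Section 11.1 asks about dominant and recessive patterns. None of these plans a 2-df association test. Section 10.5 fixes the coding explicitly, and Section 11.1 looks at the genetic model only for markers that have already passed a significant or suggestive threshold. It cannot recover effects that the additive test misses.

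**Conclusion.** The mismatch is explicit in the text and does not depend on any assumption: Section 5.1 and Figure 5-1 report power for a 2-df test, and Section 10.5 plans only a 1-df additive test. At homozygote OR 4 the 2-df figures understate additive power by about 8–11 points at RAF 0.2–0.5. They overstate power for recessive effects and for dominant effects at RAF of about 0.3 and above. For dominant effects the crossover is near RAF 0.2, and at RAF 0.1 the planned test is the better one. The sizes rest on the assumed RAF grid and the HWE baseline.

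Two stronger readings are not supported. A reader might infer that the curves in Figure 5-1 are miscalculated; they may be correct for the test they name, and the figure is not available to check. A reader might also infer that the planned test covers recessive and common dominant effects poorly in general; it has 90–98% power for dominant OR 6 at RAF 0.3, and 83–97% for recessive OR 6 at RAF 0.5.

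Type I error, thresholds and effect estimates are unaffected.

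**What to change.** - Recompute Figure 5-1 and the closing paragraph of Section 5.1 for the 1-df additive test of model (1), under the same three true models and six RAFs.
- State the baseline used (where HWE is assumed, and the prevalence if one enters).
- State whether the OR in the >80% sentence is per allele or between homozygotes.
- Name the allele frequencies and effect sizes at which the planned test has less power than the 2-df curves show: recessive effects, and dominant effects at RAF of about 0.3 and above. A general caveat would be too broad.

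The cost is one rerun of the power program, one replaced figure and one rewritten paragraph. The planned analysis does not change.

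### Section 5.1 of the SAP marks MAF of at least 20% with OR of at least 4 as the region of >80% power, but at a homozygote OR of 4 an additive effect has only about 16–35% and a dominant effect falls well below 80% at high MAF

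*SAP*

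**What the plan says.** SAP section 5.1 calculates power for the case-control endpoint "assuming a 2 degree of freedom genotypic test conditional on the underlying genetic model being additive, dominant or recessive". The alpha is 3.1×10⁻⁴, described as "the significance threshold with Bonferroni correction for Tier 1 markers". The label on Figure 5-1 repeats the inputs: "Power @ alpha=0.00031 & nca=90, nco=132, npc=0". The effect scale is given once: "The plots show the relationship between statistical power and the odds ratio (OR) of the two homozygotes".

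The conclusion begins "With 90 diarrhoea cases and 132 controls as defined in Section 2.2". It says that many combinations of model, allele frequency and odds ratio may give more than 80% power, "especially if the dominant or additive models are true and if the risk allele is relatively common in the study population". A bracket introduced by i.e. then pins this down as "MAF \geq 20% with a genetic effect OR \geq 4". The bracket does not repeat the OR scale. The section does not say whether the risk allele frequency (RAF) refers to controls or to the source population.

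The association model in section 10.5 codes genotype as 0, 1 or 2 copies of the minor allele, which is a 1-df additive test.

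**The concern.** If the OR compares the two homozygotes, an additive OR of 4 is an OR of 2 per allele. With 222 subjects and an alpha near 0.0003, 80% power for an OR of 2 per allele is implausible. The dominant part is doubtful for a different reason. As the risk allele becomes more common, non-carriers become scarce, so power for a dominant effect should fall, whereas the bracket sets no upper limit on MAF.

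Section 5.1 says its purpose is to show which genetic effects could be found, and this sentence is its conclusion. A reader could take a non-significant Tier 1 result as evidence against common variants with a homozygote OR of 4. Under the additive model, which is the one fitted, such a variant would usually miss the Tier 1 Bonferroni threshold.

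**Working it through.** **Inputs from the SAP.**
- Cases: 78 at grade 2 plus 12 at grade 3 or above = 90 (Table 5-1, PGx population). This reproduces. Controls: 132, taken as stated.
- Alpha: 0.05/3/53 = 3.14×10⁻⁴ (section 7.6), which agrees with 3.1×10⁻⁴.
- Test: 2-df genotypic chi-square, critical value 16.16. For the planned 1-df additive test the critical value is 13.01.
- Effect: homozygote OR 4. Genotype ORs are 1, 2, 4 (log-additive), 1, 2.5, 4 (linear in OR) and 1, 4, 4 (dominant).

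**Assumptions.** Hardy-Weinberg proportions, with the risk allele as the minor allele. RAF refers either to controls or to a source population with case prevalence 20% or 90/222 = 40.5%. There are no covariates and the causal variant is typed, as the SAP itself assumes.

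**Formula.** With case and control genotype frequencies p and q and pooled frequency m = (90p + 132q)/222, the Pearson non-centrality is λ = (90×132/222) × Σ(p − q)²/m = 53.51 × Σ(p − q)²/m. Power is the probability that a non-central chi-square with 2 df and non-centrality λ exceeds 16.16. Power of 80% needs λ of about 22.5.

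**Additive, OR 4, MAF 20%, RAF in controls.**
- Controls: 0.640, 0.320, 0.040.
- Case weights 0.64×1, 0.32×2, 0.04×4 sum to 1.44, giving cases 0.444, 0.444, 0.111.
- Pooled: 0.561, 0.370, 0.069.
- Σ(p − q)²/m = 0.0682 + 0.0418 + 0.0735 = 0.1835, so λ = 9.82 and power is 23%.

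**Dominant, OR 4, RAF in controls.**
- MAF 20%: case weights 0.64, 1.28, 0.16 sum to 2.08, giving cases 0.308, 0.615, 0.077; λ = 23.6, power 83%. This part of the SAP's statement reproduces.
- MAF 50%: case weights 0.25, 2.00, 1.00 sum to 3.25, giving cases 0.077, 0.615, 0.308 against controls 0.25, 0.50, 0.25; λ = 10.9, power 28%.

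**Power at homozygote OR exactly 4 (Pearson non-centrality).**

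| Model, test, RAF reference | MAF 20% | 30% | 40% | 50% |
|---|---|---|---|---|
| Log-additive, 2 df, controls | 23% | 32% | 35% | 33% |
| Log-additive, 2 df, population 40.5% | 16% | 26% | 32% | 33% |
| Linear in OR, 2 df, controls | 39% | 41% | 34% | 25% |
| Linear in OR, 2 df, population 40.5% | 34% | 42% | 40% | 32% |
| Log-additive, 1 df, controls | 32% | 43% | 46% | 43% |
| Log-additive, 1 df, population 40.5% | 23% | 36% | 43% | 44% |
| Dominant, 2 df, controls | 83% | 72% | 51% | 28% |
| Dominant, 2 df, population 40.5% | 82% | 83% | 71% | 48% |

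The highest 1-df value, with additivity linear in OR, is 51%. At 20% prevalence nearly all values lie between the two rows shown; the dominant value at MAF 20% is 84%. Likelihood-ratio non-centrality adds 1–2 points to the additive figures and up to about 6 points to the dominant ones at high MAF. Simulation with 100,000 replicates agreed to within about 3 points for the additive and dominant models.

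**Homozygote OR needed for 80% power, log-additive, 2 df.** With RAF in controls: 7.9, 6.9, 6.8 and 7.3 at MAF 20, 30, 40 and 50%. With RAF in a population at 40.5% prevalence: 10.9, 8.2, 7.3 and 7.2.

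**OR read as per allele.** A per-allele OR of 4 is a homozygote OR of 4² = 16. Additive 2-df power is then 93% or more at every MAF from 20% to 50%. The dominant figures do not change.

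**The case against.** - **The sentence is hedged.** It says that many combinations may give good power, and OR of at least 4 is open-ended. As a statement that such combinations exist, it is true: dominant OR 4 at MAF 20% reaches 80%, and so do large additive effects. A reader might infer from the table that the whole region OR of at least 4 is underpowered; that does not follow, because the low additive figures belong to OR = 4. However, the bracket marks out a region, and its lower edge is what a reader will take away.
- **The calculation itself may be right.** The curves of Figure 5-1 are not in the text at hand, and the bracket does not restate the OR scale. A reader might infer that the SAP's power calculation is wrong. The documents do not show that, since the bracket may have slipped to a per-allele OR. This stands as a limit on the finding. It does not rescue the sentence: section 5.1 defines only the homozygote scale, and a per-allele reading leaves the dominant claim failing at MAF 40–50%.
- **Power is already said to be possibly over-estimated.** The reasons given are covariates and partial linkage disequilibrium. Both would lower power further and neither explains the gap.
- **The consequences are limited.** The SAP calls all analyses exploratory and nowhere treats a null result as excluding an effect. Tier 1 markers at p ≤ 0.05 are reported as suggestive (section 7.6). At that level the 1-df test has about 88–94% power for an additive homozygote OR of 4 with RAF in controls, so such a variant would probably still be listed. This stands and lowers the severity.

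**Conclusion.** The sentence is wrong as written on the section's own OR scale. At a homozygote OR of 4 the additive model does not approach 80% power at any MAF from 20% to 50%: about 16–35% with the stated 2-df test, up to about 42% if additivity is linear in the OR, and about 23–51% with the planned 1-df test. The dominant model supports the sentence at MAF 20%, and at 30% only under some RAF conventions (72–83%). It does not at 40% (about 51–71%) or 50% (about 28–48%).

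These figures rest on Hardy-Weinberg proportions and on the RAF references listed above, which the SAP leaves open; no choice among them changes the conclusion. Severity is moderate. The power statement is retrospective, on data already collected, and nothing in the sample size, thresholds, endpoint or model depends on it.

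**What to change.** Reword the conclusion of section 5.1 so that it names the OR scale, the test and the RAF reference population, and claims >80% only where it is reached. For example:

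> With the 2-df test, RAF taken in controls and the OR comparing the two homozygotes, a dominant OR of 4 has >80% power near RAF 20%, declining at higher RAF. An additive OR of 4 has about 23–35% power at RAF 20–50%; 80% power needs an OR of about 7–8. A non-significant Tier 1 result does not exclude an additive homozygote OR of 4.

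If the OR was meant per allele, say so in the sentence and still correct the dominant statement at high RAF. Check the new wording against the curves in Figure 5-1.

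The cost is a change of SAP wording and a less favourable stated power. The analysis is unaffected.
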